#### AE Counting Rules:

Where a patient has the same AE, based on PT, reported multiple times in a single analysis period, the patient will only be counted once at the PT level in AE frequency tables.

Where a patient has multiple AEs within the same SOC in a single analysis period, the patient will only be counted once at the SOC level in AE frequency tables.

When a patient has the same AE, based on PT, reported multiple times in a single analysis period, the following criteria, in order of precedence, will be used to select the event to be included in summary tables:

- Relationship to study treatment
- Intensity of event
- Onset date and time

When reporting AEs by intensity, in addition to providing a summary table based on the event selection criteria detailed above, summary tables will also be provided based on the most intense event during the analysis period - independent of relationship to study treatment. For these tables, the following criteria, in order of precedence, will be used to select the event to be included in summary tables:

- Intensity of event
- Onset date and time

Patients will only be counted once in the 'Total' at their maximum intensity, regardless of SOC or PT.

#### **7.6.4 Clinical Laboratory Evaluations**

The results of all protocol-specified clinical laboratory tests will be listed by patient for the safety population. Laboratory measurements and corresponding change from baseline values will be summarized by treatment and scheduled nominal visit for each laboratory test.

Laboratory evaluations will be reported both in conventional units and in SI units.

Laboratory results will be classified as markedly abnormal based on sponsor defined criteria. The criteria used for classifying laboratory test results as markedly abnormal will be listed. Laboratory results for patients with any marked laboratory abnormality (scheduled and unscheduled) will be listed. This listing will include all observations for the specific laboratory test and patient, not only the marked laboratory abnormality measurements. The frequency of patients with any marked laboratory abnormality, based on pre-specified criteria, will be presented.

#### **7.6.5 Electrocardiograms**

All recorded ECGs will be listed for the safety population.

If QT corrected for heart rate (HR) using Fridericia formula (QTcF) is not available in the database, QTcF will be calculated using the reported uncorrected QT Interval and HR, and the following formula:

$$QTcF = \frac{QT}{60 \text{ HEART RATE}}^{1/3}$$

Summaries of ECG parameters (HR, QT, QTcF, PR, and QRS intervals) will be tabulated by study day and treatment. Summaries of ECG parameters will include change from baseline on Days 1, 5, 8, and 12.

Patients with ECG intervals outside of a pre-specified range and investigator identified ECG abnormalities will also be listed.

The following criteria will be used to determine ECG results that are outside of a pre-specified range:

PR (msec):	Value > 200
QRS (msec):	Value > 120
QT (msec):	Value > 500 or change from baseline > 30
QTcF (msec):	Value > 450 or change from baseline > 30

### 7.6.6 Vital Signs

Vital signs parameters (systolic blood pressure [BP], diastolic BP, HR, respiratory rate, and body temperature) will be listed. Summaries of vital sign parameters (HR and BPs) will be provided for each vital sign parameter at corresponding visits by treatment and respective changes from baseline. Baseline for HR and BPs is defined as the last non-missing result with a collection date-time less than the date-time of the active dose of study treatment within each treatment period.

Patients with vital signs outside of a pre-specified range will also be listed.

The following criteria will be used to determine vital sign results that are outside of a pre-specified range, where changes from baseline are based on matched postural positions and are calculated as parameter value - baseline parameter value:

Heart Rate (bpm)	Value > 100 and change from baseline > 30, or Value < 55 and change from baseline < -15
Systolic BP (mmHg)	Value > 140 and change from baseline > 20, or Value < 90 and change from baseline < -20
Diastolic BP (mmHg)	Value > 90 and change from baseline > 10, or Value < 55 and change from baseline < -10
Respiration (breaths/min)	Value > 16 or change from baseline > 10
Temperature (°C)	Value > 38.3°C or change from baseline > 1.6°C

### 7.6.7 *Physical Examination Findings*

All PE abnormal findings will be listed per patient and visit.

### 7.7 Pharmacokinetics

The PK population will be used for all listings. Evaluable PK population will be used for summary statistics and statistical analyses. Analysis will include all valid data in the PK dataset for BMS-986177.

Patient plasma concentration-time profiles will be listed and summarized by treatment and nominal collection time. Plot of individual plasma concentration profiles over time will be provided. Overlay of individual plasma concentration profiles over time will be provided by treatment. Plots of mean (+SD) plasma concentration profiles versus time will be presented, and all treatments will be superimposed on the same plot.

Dialysate recovery data will be listed. Cumulative amount and cumulative percent recovered per interval will be summarized.

All individual PK parameters will be listed including any exclusions and reasons for exclusion. Summary statistics will be tabulated for each PK parameter by treatment. Geometric means and %CV will be presented for Cmax, AUC(0-T), AUC(INF), AUC(0-48), Cmaxfu, AUC(0-T)fu, AUC(INF)fu, AUC(3-7), and CLD. Medians and ranges will be presented for Tmax. Means and SDs will be presented for other PK parameters (ie, T-HALF, fu and %DR). Decimal place specifications for summary statistics are described in [Section 7.10](#).

### 7.8 Pharmacodynamics

The PD population will be used for all listings, summary statistics and figures. Summary statistics will be tabulated for aPTT, FXIc, and anti-Xa assessments and percent changes from baseline by treatment and time point. Plots of mean + standard error (SE) values and percent changes from baseline for aPTT will be provided. In addition, the relationship between aPTT and FXIc percent change from baseline and BMS-986177 plasma concentrations will be explored graphically via scatter plots by treatment.

The baseline for aPTT, FXIc and anti-Xa is defined as the predose value on day of dosing for each treatment.

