5. STUDY DESIGN

5.1 Overall Design

This study is a multicenter, cross-over, randomized, open-label trial with blinded endpoint assessment investigating safety and tolerability of single oral doses of BMS-986177 in patients with ESRD undergoing chronic stable HD three times per week. Secondary objectives are to assess BMS-986177 pharmacokinetics and hemodialysis success defined as completion of hemodialysis without premature interruption of the procedure due to complete clotting of the dialytic circuit and/or filter.

Study treatments will be administered on the first and last HD day of the week (either Monday and Friday, or Tuesday and Saturday, depending on the patients HD schedule), for a total of 4 treatment days (2 doses of BMS-986177, 1 dose of UFH, 1 dose of Enoxaparin).

The 2nd HD day of the week is not a study treatment day; on that day, study patients will undergo dialysis with standard of care, as per their schedule, and no study activities will be performed on those days.

Screening for inclusion in the study will be performed up to 28 days before the first study visit. After screening and meeting eligibility as per inclusion and exclusion criteria, patients will be randomized to 1 of following 4 sequences that will be conducted in parallel.

Sequence No.	Period			
	1	2	3	4
1	UFH	BMS dose 1 (BMS-986177 100 mg)	BMS dose 2 (BMS-986177 300 mg)	Enoxaparin
2	BMS dose 1 (BMS-986177 100 mg)	Enoxaparin	UFH	BMS dose 2 (BMS-986177 300 mg)
3	BMS dose 2 (BMS-986177 300 mg)	UFH	Enoxaparin	BMS dose 1 (BMS-986177 100 mg)
4	Enoxaparin	BMS dose 2 (BMS-986177 300 mg)	BMS dose 1 (BMS-986177 100 mg)	UFH

Note: Per amendment/revised protocol 01, the BMS-986177 doses will be 100 mg (BMS dose 1) and 300 mg (BMS dose 2).

Clinical Protocol
BMS-986177

CV010010
FXIa

Study patients will be admitted to the study facility the same day of HD treatment day or the night before. Assessment of vital signs and clinical biochemistry will be performed pre-dose.

Study treatments will be administered:

- BMS-986177: one single oral dose 3 hours prior beginning the HD session
- UFH: I.V. infusion to start within 10 minutes prior beginning the HD session. The dosage and duration of UFH use are at the discretion of the physicians and are per their institutional practice.
- Enoxaparin: one single dose (40 mg) by subcutaneous injection 3 hours prior beginning the HD session

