7.7 Concomitant Therapy

7.7.1 Prohibited and/or Restricted Treatments

Prohibited and/or restricted medications taken prior to study drug administration in the study are described below. Medications taken within 4 weeks prior to study drug administration must be recorded on the CRF.

- 1) Use of any agent, including but not limited to anti-platelet agents (except aspirin), anticoagulants (except heparin for routine hemodialysis use), fish oil capsules, and ginkgo that is known to increase the potential for bleeding within 2 weeks prior to study drug administration. Use of non-steroidal anti-inflammatory compounds (NSAIDs) or aspirin within 1 week prior to study drug administration.
- 2) Exposure to any investigational drug or placebo within 4 weeks of study drug administration.
- 3) Use of acid controllers within two days of BMS-986177 study drug administration except those medications cleared by the BMS medical monitor. The use of acid controllers after BMS-986177 administration and after hemodialysis is allowed. The use of acid controllers is also allowed when enoxaparin or UFH are administered.
 - a) Sodium bicarbonate is allowed during the study.
- 4) Use of strong and moderate CYP3A inhibitors within 1 week of enrollment including the following: the antifungals and antibiotics ketoconazole, fluconazole, itraconazole, miconazole, clotrimazole, erythromycin and clarithromycin; the calcium channel blockers diltiazem and verapamil; the HIV anti-virals delaviridine, indinavir, nelfinavir, ritonavir, and saquinavir; and the serotonin reuptake inhibitor fluoxetine. Use of CYP3A inducers such as carbamazepine, dexamethasone, phenobarbital, phenytoin, rifampin, St John's Wort within 4 weeks of enrollment. Topical antifungal use is allowed.

Study patients may receive treatment with medications necessary for maintaining the clinical status of their condition as described in Inclusion Criteria.

Any concomitant therapies must be recorded on the CRF.

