#### 4.4 Pharmacodynamic Endpoints

The PD endpoints include aPTT and FXIc for BMS-986177, aPTT and anti-Xa for heparin and enoxaparin.

[REDACTED]

[REDACTED]

[REDACTED]

[REDACTED]

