### Handling of Non-Quantifiable Concentrations

For the summaries of plasma concentration-time data, concentrations that are less than the lower limit of quantification (LLOQ) should be displayed as “< LLOQ” in the listings and be treated as missing in summary tables and plots. For the purpose of calculating PK parameters, pre-dose concentrations that are less than LLOQ and concentrations prior to the first quantifiable concentration that are less than LLOQ will be set to 0, and all other concentrations less than LLOQ will be set to missing.

Summary statistics for analyses of PD/biomarker-concentrations will be calculated by imputing values less than LLOQ as  $\frac{1}{2} * \text{LLOQ}$ .

All available plasma concentration-time data and derived PK parameter values will be included in the PK data set and listed accordingly.

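### Percent change in anti-Xa divides by a pre-dose value that is likely to be near or below the assay limit, so its size depends heavily on that limit

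*SAP*

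**What the plan says.** SAP 4.4 gives the pharmacodynamic endpoints for the comparators as "aPTT and anti-Xa for heparin and enoxaparin", and Protocol 9.6 schedules anti-Xa on UFH and enoxaparin days only. SAP 7.8 plans the summary: "Summary statistics will be tabulated for aPTT, FXIc, and anti-Xa assessments and percent changes from baseline by treatment and time point". It also fixes the denominator: "The baseline for aPTT, FXIc and anti-Xa is defined as the predose value on day of dosing for each treatment".

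The rule for low values is in SAP 7.10.2, under the handling of non-quantifiable concentrations: "Summary statistics for analyses of PD/biomarker-concentrations will be calculated by imputing values less than LLOQ as" one half of the LLOQ. Neither section makes an exception for anti-Xa or for a value used as a baseline.

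Three parts of the design bear on the pre-dose level:

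- Protocol 7.7.1 restricts anticoagulants in the two weeks before study drug, except heparin for routine dialysis.
- On the middle dialysis day of each week, Protocol 5.1 says that "on that day, study patients will undergo dialysis with standard of care".
- UFH on its study day is an "I.V. infusion to start within 10 minutes prior beginning the HD session" (Protocol 5.1), while Protocol Table 9.6-2 labels the single 00:00 sample as both pre-dose and start of dialysis.

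**The concern.** Percent change is informative when the baseline is a stable, well-measured quantity, as one expects for aPTT and FXIc. Anti-Xa activity before a heparin dose should be close to nothing if the previous dialysis anticoagulant has worn off. Dividing by a value near zero, or by a placeholder for one, gives a number whose size is set largely by the placeholder.

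Two things are at stake. The percent-change means and SDs for both comparators could not be interpreted without knowing the LLOQ and how many baselines fell below it, and SAP 7.8 does not ask for that count. And where some patients are just above the limit and others below it, the table would show large between-patient differences that do not exist in the on-treatment anti-Xa level.

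**Working it through.** Neither document gives a figure for anti-Xa, so there is none to reproduce. All anti-Xa levels and LLOQs below are assumptions, in IU/mL.

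**1. Time since the previous dialysis session.** The schematic (Protocol Figure 5.1-1) puts dialysis on Days 1, 3, 5, 8, 10 and 12, so sessions start 48 or 72 hours apart. Assume constant start times and 4-hour sessions. Enoxaparin is given 3 hours before dialysis, so the shortest gap from the end of one session to the next enoxaparin pre-dose sample is 48 − 4 − 3 = 41 hours. For a UFH-day sample at the start of dialysis it is 48 − 4 = 44 hours.

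**2. Percent change with a baseline below LLOQ.** With baseline b and on-treatment value x, percent change is 100 × (x − b)/b. Setting b = LLOQ/2 gives 100 × (2x/LLOQ − 1). For x = 0.5:

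| Assumed LLOQ | Baseline used | Percent change | Absolute change |
|---|---|---|---|
| 0.02 | 0.01 | +4900% | 0.49 |
| 0.05 | 0.025 | +1900% | 0.475 |
| 0.1 | 0.05 | +900% | 0.45 |
| 0.2 | 0.1 | +400% | 0.40 |

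Over a 10-fold range of LLOQ, percent change moves 4900/400 = 12.25-fold. Absolute change moves 0.49/0.40 = about 1.2-fold.

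**3. Mixed baselines at one LLOQ (0.1).**

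- Reaching 0.5 from an imputed 0.05: 100 × (0.5/0.05 − 1) = +900%.
- Reaching 0.5 from a measured 0.12: 100 × (0.5/0.12 − 1) = +317%.
- Reaching only 0.3 from an imputed 0.05: 100 × (0.3/0.05 − 1) = +500%, above the +317% of the patient who reached 0.5. Patient ordering is reversed.

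**4. Effect on the mean and SD.** Take 24 patients who all reach 0.5, with 20 baselines below LLOQ 0.1 and 4 measured at 0.12. The mean is (20 × 900 + 4 × 316.7)/24 = 803%. The two values differ by 583.3 points, so the sample SD is 583.3 × √[(20/24)(4/24)(24/23)] = 222 points, although on-treatment levels do not vary at all. Absolute changes are 0.45 and 0.38, and their SD is 0.07 × √[(20/24)(4/24)(24/23)] = 0.027.

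**5. When the problem fades.** A simulation (200,000 draws) used log-normal values: on-treatment median 0.4 with log-SD 0.4, and pre-dose log-SD 0.7. The LLOQ was varied from 0.02 to 0.2.

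| Assumed pre-dose median | Baselines below LLOQ | Mean percent change |
|---|---|---|
| 0.01 | 84% to 100% | 3790% down to 330% |
| 0.1 | 1% to 84% | between 286% and 517% |
| 0.2 | 0% to 50% | between 177% and 209% |

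With a pre-dose median of 0.01 the LLOQ largely fixes the mean. With 0.2 it hardly matters.

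**The case against.** The strongest reply is that the premise is not in the documents. They give no anti-Xa LLOQ, no pre-dose level and no expected share below LLOQ. A reader might infer that the baseline will usually be unquantifiable. The washout interval and the anticoagulant restrictions make that likely, but they do not establish it, and step 5 shows that the conclusion depends on it. This stands, and the point is conditional on it.

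A reader might also infer that percent change would reflect the assay and not the drug. The documents do not support that either. If every baseline is below one fixed LLOQ, percent change is a linear rescaling of the on-treatment value. The time course and the ordering of UFH against enoxaparin survive, and only the scale is arbitrary. Ordering is lost only with mixed baselines, as in step 3.

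The half-LLOQ rule sits under pharmacokinetic summaries and speaks of concentrations. It names neither anti-Xa activity nor its use as a denominator, and table details are left to a Data Presentation Plan that is not available here. Applying it to anti-Xa is the natural reading, not an explicit one. If it does not apply, however, the SAP has no rule. A zero baseline would leave percent change undefined, and a missing one would restrict the summary to patients with residual activity.

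On UFH days the 00:00 sample, if drawn at the start of dialysis, could already contain UFH, so that baseline need not be low. This is fair, but such a baseline would not be pre-dose and would not be comparable with the enoxaparin one.

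Finally, the consequences are limited. The same sentence of SAP 7.8 tabulates observed anti-Xa, SAP 7.1 adds median, minimum and maximum, no anti-Xa plot is named in SAP 7.8, and no formal hypothesis is tested. All of that stands.

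**Conclusion.** The point holds in conditional form. For any baseline imputed at half the LLOQ, the size of the percent change depends heavily on the assay limit: about 12-fold over a 10-fold range of assumed LLOQ, against about 1.2-fold for absolute change. If baselines fall on both sides of the limit, equal on-treatment levels give figures as far apart as +317% and +900%, which distorts the mean and SD. The conclusion rests on pre-dose values near or below LLOQ, which the design makes likely, and on the half-LLOQ rule applying to anti-Xa. It fades if most pre-dose values are well above LLOQ.

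The effect is confined to a misleading percent-change table for the two comparators. Anti-Xa is descriptive, and the primary safety conclusions do not use it. The case for changing the plan is that the remedy costs almost nothing and loses no useful information.

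**What to change.** In SAP 7.8, summarise anti-Xa as observed value and absolute change from baseline, report the number of values below LLOQ at each time point including baseline, and limit percent change to aPTT and FXIc. State there that the half-LLOQ rule of SAP 7.10.2 applies to anti-Xa, if that is intended.

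Reconcile the 00:00 label in Protocol Table 9.6-2 with the infusion timing in Protocol 5.1, and record whether the UFH-day baseline is drawn before the infusion starts. Absolute change also needs a baseline that is truly pre-dose.

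The cost is one SAP sentence, a clarification of sample timing, and the loss of the anti-Xa percent-change column.

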### 7.10 Conventions

Analysis Data Model (ADaM) standards will be applied.

#### 7.10.1 *Decimal Places*

The number of decimal places displayed in all listings will be determined by the number of decimal places in the raw data.

Unless otherwise specified, minimum and maximum will be reported to the precision as the data collected, 1 more decimal place for the mean, median, and SD, and 2 more decimal places for the SE. The geometric mean ratio and the lower and upper limits of confidence interval will be displayed to 3 decimal places.

For percent change from baseline data, minimum and maximum will be reported with 0 decimal places, mean, median, and SD will be reported with 1 decimal place, and SE will be reported with 2 decimal places.

The incidence rate will be rounded to 1 decimal place. If the incidence rate is less than 0.1%, then “<0.1” will be displayed.

Three decimal places for ratio will be used for data presentation.

#### 7.10.2 *Pharmacokinetic Summaries*

##### In-text Tables

For in-text PK tables, %CV will be reported as integers. For other statistics except for SDs, values of 100 or higher will be presented as integers, values of 10 - <100 will be displayed to 1 decimal place, and values of 1 - < 10 will be displayed to 2 decimal places. Values less than 1 will be displayed to 3 decimal places. Ratios will also be displayed to 3 decimal places. Standard deviations will be reported to a precision of 1 decimal place more than the mean.

### Handling of Non-Quantifiable Concentrations

For the summaries of plasma concentration-time data, concentrations that are less than the lower limit of quantification (LLOQ) should be displayed as “< LLOQ” in the listings and be treated as missing in summary tables and plots. For the purpose of calculating PK parameters, pre-dose concentrations that are less than LLOQ and concentrations prior to the first quantifiable concentration that are less than LLOQ will be set to 0, and all other concentrations less than LLOQ will be set to missing.

Summary statistics for analyses of PD/biomarker-concentrations will be calculated by imputing values less than LLOQ as  $\frac{1}{2} * \text{LLOQ}$ .

All available plasma concentration-time data and derived PK parameter values will be included in the PK data set and listed accordingly.

### Treatment of Outliers

Individual plasma concentrations, if deemed to be anomalous, may be excluded from the analysis following a review of available documentation (eg, bioanalytical report, clinical data). Any such exclusion will be clearly listed in the study report along with justification for exclusion.

Entire plasma concentration-time profiles for a patient may be excluded follow review of available documentation (eg, bioanalytical report, clinical data). However, results of analysis with and without the excluded profiles may be presented in the study report. Any such exclusion will be clearly listed in the study report along with justification for exclusion.

### Pharmacokinetic Exclusions

Pharmacokinetic Analysis, Reporting, and Exclusion criteria should following the BMS PK Harmonization document Version 2.0. Specific guideline for exclusionary criteria for half-life and how other PK parameters are affected for exclusion is under section 6.2 of the BMS PK Harmonization document.

Exclusion of 1 or more parameters or the entire dataset may be considered due to an incomplete profile such as AUC(INF) or when T-HALF cannot be reliably calculated, or there is no sample around the suspected Cmax. In addition, patients may be excluded from the analysis if they missed doses, had diarrhea, or vomited at or before a time equal to twice the median Tmax for immediate-release products, or vomited at any time during sampling after the administration of modified-release formulations.

## **8 CONTENT OF REPORTS**

Statistical components for the CSR will be based on the content of this statistical analysis plan. Details of the tables, listings, and figures to be prepared for the final CSR will be included in a study-specific Data Presentation Plan.

